## **10.10 Resistance Analyses**

If possible, subjects treated with study drug during the Treatment Period who experience virologic failure will have resistance testing conducted if 1) they have on-treatment breakthrough; 2) if they have post-treatment relapse, with a study drug duration  $\geq$  77 days for subjects assigned to 12 weeks of treatment or with a study drug duration  $\geq$  154 days for subjects assigned to 24 weeks of treatment; or 3) if they have at least 6 weeks of treatment and fail to suppress by Week 6 (i.e., meet virologic stopping criteria). Subjects meeting one of these criteria will be referred to as subjects in the primary virologic failure (PVF) population, and a listing by subject that includes HCV subtype, IL28B genotype, reason for non-response, time point(s) sequenced as closest to time of VF, and HCV RNA value at the VF time point(s) will be produced for these subjects. In addition, all listings described below will display HCV subtype and reason for non-response in the subject identifier for each subject. A separate listing will delineate all subjects in the PVF population for whom no sequencing was performed (e.g., lost to follow-up while HCV RNA  $\leq$  1000 IU/mL).

Only samples with an HCV RNA level of  $\geq$  1000 IU/mL will undergo sequence analysis in order to allow accurate assessment of products of amplification. Therefore if the HCV RNA level at the time of virologic failure (VF) is  $<$  1000 IU/mL, the sample closest in time after the failure with an HCV RNA level  $\geq$  1000 IU/mL will be used if available.

The regions of interest for population sequencing from all evaluated time points in this study are those encoding full length NS3/4A, NS5A, and NS5B. The prototypic reference sequences used for analysis will be H77 for genotype 1a or Con1 for genotype 1b.

For each DAA target, resistance-associated signature amino acid variants will be identified by AbbVie Clinical Virology. Amino acid positions where resistance

associated variants have been identified in vitro and/or in vivo are 1) for ABT-450: 36, 43, 55, 56, 80, 155, 156, and 168 in NS3 for genotype 1a; 55, 56, 155, 156, and 168 in NS3 for genotype 1b; 56, 155, 156, and 168 for genotype 4; 2) for ABT-267: 24, 28, 29, 30, 31, 32, 58, 62, 92, and 93 in NS5A for genotype 1a; 24, 28, 29, 30, 31, 32, 58, 62, 92, and 93 in NS5A for genotype 1b; 28, 30, 31, 58, and 93 for genotype 4; and 3) for ABT-333: 316, 414, 446, 448, 451, 553, 554, 555, 556, 558, 559, and 561 in NS5B for genotype 1a; 316, 368, 411, 414, 445, 448, 553, 556, and 559 in NS5B for genotype 1b. The final list of amino acid positions where resistance-associated variants have been identified will be included in the CSR.

The following definitions will be used in the resistance analyses:

- Baseline variant: a variant (by population sequencing) in a baseline sample determined by comparison of the amino acid sequence of the baseline sample to the appropriate prototypic reference amino acid sequence for a given DAA target (NS3, NS5A, or NS5B).
- Post-baseline variant by population sequencing: an amino acid variant in a post baseline time point sample that was not detected at baseline in the subject and is detectable by population sequencing.
- Emerged variant by population sequencing: a post-baseline variant that is observed in 2 or more subjects of the same subtype by population sequencing.
- Linked variant by population sequencing: 2 or more signature resistance associated or emerged amino acid variants identified within a target by population sequencing, and no mixture of amino acids is detected at either position.

The following analyses will be performed on the samples from subjects who are in the PVF population and have baseline and post-baseline resistance data available.

The HCV amino acid sequence as determined by population sequencing at baseline will be compared to the appropriate prototypic reference amino acid sequence. A listing by subject of all baseline variants relative to prototypic reference sequence at signature

resistance-associated amino acid positions will be provided for each DAA target (NS3, NS5A, and NS5B – genotype 1 only).

The HCV amino acid sequence as determined by population sequencing at the time of VF or the sample closest in time after VF with an HCV RNA level of  $\geq 1000$  IU/mL will be compared to the baseline and appropriate prototypic reference amino acid sequences. A listing by subject and time point of all post-baseline variants relative to the baseline amino acid sequences will be provided across all DAA targets (NS3, NS5A, and NS5B). In addition, a listing by subject and time point of all post-baseline variants at signature resistance amino acid positions relative to the appropriate reference sequence will be provided across all DAA targets (NS3, NS5A, and NS5B – genotype 1 only).

The number and percentage of subjects with post-baseline variants at signature amino acid positions or emerged variants at non-signature amino acid positions by population sequencing, listed by amino acid position and variant within a DAA target at the time of VF compared to baseline will be summarized, along with the number of subjects within a DAA target and overall. The analyses will be grouped by HCV subtype and DAA target (NS3, NS5A, or NS5B – genotype 1 only) and will list the numbers of subjects with each variant. The number of subjects with resistance variants in 3 targets – (genotype 1 only), 2 targets or 1 target will also be provided.

Linkage between emerged or signature variants by population sequencing will also be evaluated. A listing by subject and time point of the linked variants by population sequencing for each target will be provided.

For all subjects who experience VF, the persistence of resistance-associated variants for each target (NS3, NS5A, and NS5B – genotype 1 only) will be assessed by population sequencing at Post-Treatment Week 24. Listings by subject of all treatment emergent variants at signature resistance-associated positions will be provided for each DAA target.

---

**10.11                   Patient Reported Outcomes**

During Treatment and Post-Treatment, health utility values will be assessed using the EQ-5D-3L instrument. The health state data measured by EQ-5D-3L will be analyzed using adult weights until validated weights are available for pediatric subjects to convert health states to a single summary index.

Subject's responses to the EQ-5D-3L will be combined into a unique health state using a 5-digit code with 1 digit from each of the 5 dimensions. The EQ-5D-3L states will be converted into a single preference-weighted health utility index score by applying country-specific weights (if available) or US weights (if not available). The VAS score will be analyzed separately.

For subjects enrolled in Part 1 and 2 (ITT), summary statistics at each visit and on the change from baseline to each visit (n, mean, SD, median, minimum and maximum) of EQ VAS score will be provided overall and by age group. In particular, for each of the three visits – EOT, PT Week 12 and PT Week 24, the mean change from baseline in EQ VAS score, will be compared between subjects who achieve SVR12 and those who do not using ANCOVA with SVR12 status as a factor, and appropriate baseline fibrosis stage, gender, age group, and EQ VAS score as covariates. Point estimate of the mean difference and 95% confidence intervals will be provided using the subjects who do not achieve SVR12 as the reference group. For subjects enrolled in Part 3 (ITT-3), summary statistics at each visit after PT Week 24 and the change from baseline to each applicable visit after PT Week 24 (n, mean, SD, minimum and maximum) in EQ VAS score will be provided. The ANCOVA analyses will be performed only if there is a sufficient number of subjects who didn't achieve SVR12.

**10.12                   Acceptability Questionnaires**

The analyses of acceptability questionnaires will be performed among subjects who received the mini-tablet in the ITT population.

The number and percentage of subjects with each categorical answer marked will be presented for each question in the acceptability questionnaire at each applicable treatment visit overall, and by age and weight group. Listings of acceptability questionnaire results and comments for each applicable subject over applicable treatment visits will be produced separately for each formulation.

## **11.0 Safety Analysis**

### **11.1 General Considerations**

The safety analysis will be carried out for all subjects in the safety population using the safety population table format.

### **11.2 Analysis of Adverse Events**

#### **11.2.1 Treatment-Emergent Adverse Events**

Adverse events will be coded using the Medical Dictionary for Regulatory Activities (MedDRA). Treatment-emergent adverse events are defined as any event that begins or worsens in severity after initiation of study drug through 30 days after the last dose of study drug. Events where the onset date is the same as the study drug start date are assumed to be treatment-emergent. If an incomplete onset date was collected for an adverse event, the event will be assumed to be treatment-emergent, unless there is other evidence that confirms that the event was not treatment-emergent (e.g., the event end date was prior to the study drug start date).

##### **11.2.1.1 Tabulations of Treatment-Emergent Adverse Events**

Adverse event data will be summarized and presented using primary MedDRA system organ classes (SOCs) and preferred terms (PTs) according to the version of the MedDRA coding dictionary used for the study at the time of database lock. The actual version of the MedDRA coding dictionary used will be noted in the clinical study report. The system organ classes will be presented in alphabetical order and the preferred terms will be presented in alphabetical order within each system organ class.

## **Adverse Event Overview**

An overview of adverse events will be presented consisting of the number and percentage of subjects experiencing at least one event for the following adverse event categories:

- Any treatment-emergent adverse event;
- Treatment-emergent adverse events with a "reasonable possibility" of being related to DAAs;
- Treatment-emergent adverse events with a "reasonable possibility" of being related to RBV;
- Treatment-emergent adverse events of grade 3 or higher;
- Treatment-emergent adverse events of Grade 3 or higher with a "reasonable possibility" of being related to DAAs
- Serious treatment-emergent adverse events;
- Treatment-emergent adverse events leading to discontinuation of study drug;
- Treatment-emergent adverse events leading to interruption of study drug;
- Treatment-emergent adverse events leading to RBV dose modifications;
- Treatment-emergent adverse events leading to death;
- Deaths.

## **Adverse Event by SOC and PT**

The following summaries of adverse events will be generated:

- Treatment-emergent adverse events;
- Treatment-emergent adverse events with a "reasonable possibility" of being related to DAAs;
- Treatment-emergent adverse events with a "reasonable possibility" of being related to RBV;
- Serious treatment-emergent adverse events;
- Grade 3 or higher treatment-emergent adverse events;

---

- Treatment-emergent adverse events of Grade 3 or higher with a "reasonable possibility" of being related to DAA;
- Treatment-emergent adverse events leading to discontinuation of study drug;
- Treatment-emergent adverse events leading to interruption of study drug;
- Treatment-emergent adverse events leading to RBV dose modifications;
- Treatment-emergent adverse events leading to death;
- Treatment-emergent adverse events leading to concomitant medication use (events with other action taken of "concomitant medication prescribed").

For all adverse event summaries, the number and percentage of subjects experiencing treatment-emergent adverse events will be tabulated according to SOC and PT. Subjects reporting more than one adverse event for a given PT will be counted only once for that term (most severe incident for the severity tables and most related incident for the relationship tables). Subjects reporting more than one adverse event within a SOC will be counted only once for that SOC. Subjects reporting more than one adverse event will be counted only once in the overall total.

A listing of treatment-emergent adverse events grouped by body system and preferred term with subject numbers will be created.

### **Adverse Event by PT**

The number and percentage of subject experiencing treatment-emergent adverse events will be tabulated according to preferred term and sorted by overall frequency. Similar summaries will be provided for Grade 3 or higher treatment-emergent adverse events, DAA related treatment-emergent adverse events, and treatment-emergent adverse events of Grade 3 or higher with a "reasonable possibility" of being related to DAA.

### **Adverse Event of Special Interest**

Specific AEs of special interest will be identified by the following search criteria:

---

Adverse Event of Special Interest	Search Criteria	Time Frame
Hepatic decompensation and hepatic failure	PMQ "Hepatic decompensation and hepatic failure"	Treatment-emergent
Hepatocellular carcinoma	Cases will be identified by the following MedDRA preferred terms: hepatic cancer recurrent, hepatocellular carcinoma, hepatic neoplasm, hepatic cancer, and hepatic cancer metastatic	All post-baseline cases including both treatment emergent and non-treatment emergent
Severe cutaneous reactions	SMQ "Severe cutaneous adverse reactions" (narrow search)	Treatment-emergent

---

For each AE of special interest, the number and percentage of subjects experiencing at least one adverse event of special interest will be presented by SOC and PT. A listing of adverse events for subjects meeting the search criterion will be provided for each adverse event of special interest.

### **Adverse Event by Maximum Severity Grade Level**

Treatment-emergent adverse events and DAA-related treatment emergent adverse events will be summarized by maximum severity grade level. Each adverse event will be assigned a grade level (grade 1, 2, 3, 4, or 5) by the investigator. If a subject has an AE with unknown severity, then the subject will be counted in the severity grade level category of "unknown," even if the subject has another occurrence of the same event with a severity present. The only exception is if the subject has another occurrence of the same AE with the highest grade level (grade 5). In this case, the subject will be counted under the "Grade 5" category.

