### **6.1.3 Relationship to Study Drug**

The investigator will use the following definitions to assess the relationship of the adverse event to the use of (OBV/PTV/RTV with or without DSV) and to the use of RBV (if applicable):

- Reasonable Possibility** An adverse event where there is evidence to suggest a causal relationship between the study drug and the adverse event.

**No Reasonable Possibility** An adverse event where there is no evidence to suggest a causal relationship between the study drug and the adverse event.

For causality assessments, events assessed as having a reasonable possibility of being related to the study drug will be considered "associated." Events assessed as having no reasonable possibility of being related to study drug will be considered "not associated." In addition, when the investigator has not reported a causality or deemed it not assessable, AbbVie will consider the event associated.

[figure not shown]
If an investigator's opinion of no reasonable possibility of being related to study drug is given, an "Other" cause of event must be provided by the investigator for the serious adverse event.

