### **Adverse Event by Maximum Relationship**

Treatment-emergent adverse events also will be summarized by maximum relationship of each preferred term to DAA study drug and RBV, as assessed by the investigator. If a subject has an adverse event with unknown relationship, then the subject will be counted in the relationship category of "unknown," even if the subject has another occurrence of the same event with a relationship present. The only exception is if the subject has

another occurrence of the same adverse event with a relationship assessment of "Reasonable Possibility." In this case, the subject will be counted under the "Reasonable Possibility" category.

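### Missing grades and missing causality: the SAP's maximum-severity tables can drop a known Grade 3 or 4 event from its row, and its drug-related counts do not carry over the protocol's rule for unreported causality

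*SAP*

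**What the plan says.** **Severity.** SAP 11.2.1.1 (Adverse Event by Maximum Severity Grade Level) expects complete grading: "Each adverse event will be assigned a grade level (grade 1, 2, 3, 4, or 5) by the investigator". If a grade is missing all the same, the subject goes to an 'unknown' category "even if the subject has another occurrence of the same event with a severity present". The one exception is another occurrence of the same event at Grade 5. Under Adverse Event by SOC and PT, the SAP counts a subject once per preferred term, taking the "most severe incident for the severity tables and most related incident for the relationship tables".

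The SAP also plans separate high-grade summaries: "Treatment-emergent adverse events of grade 3 or higher" in the Adverse Event Overview, "Grade 3 or higher treatment-emergent adverse events" by SOC and PT, and a similar summary by PT. No rule for ungraded events is stated for these.

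**Causality.** Protocol 6.1.3 says that "when the investigator has not reported a causality or deemed it not assessable, AbbVie will consider the event associated". SAP 11.2.1.1 (Adverse Event by Maximum Relationship) says: "If a subject has an adverse event with unknown relationship, then the subject will be counted" as 'unknown', unless another occurrence of the same event was rated 'Reasonable Possibility'. That table reports the investigator's assessment. The DAA-related and RBV-related lines in the Overview and the SOC/PT tables are defined by a 'reasonable possibility' of being related; the PT tables repeat the DAA-related summary. Nowhere does the SAP mention the protocol's rule for missing causality.

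**The concern.** The two severity instructions give different answers for a child with one Grade 3 or 4 occurrence and one ungraded occurrence of the same term. If the 'unknown' rule is followed, the table tells the reader less than the database holds: the child is known to have reached at least Grade 3 or 4. The maximum-severity table is also the only planned adverse event table that separates Grade 3 from Grade 4, because the other high-grade summaries pool Grade 3 and above. It is how the SAP delivers the tabulation by individual grade promised in Protocol 8.1.6.1.

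On causality, the protocol gives a default for missing assessments and the SAP's tables apply a different one. A reader who knows the protocol would expect such events to be inside the drug-related counts.

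Safety is part of a primary objective in this single-arm pediatric study, and the safety tables show mini-tablet subjects by age group (SAP 5.1.2). In columns that small, one reclassified child is visible.

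**Working it through.** The documents state no figure on this point, so the check is to apply each rule to the possible combinations and then size one subject.

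**Step 1. Severity, two occurrences of the same preferred term.**

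| Occurrences | Most severe known grade (SOC and PT text) | Maximum Severity Grade Level text |
|---|---|---|
| ungraded + Grade 1 | Grade 1 | unknown |
| ungraded + Grade 2 | Grade 2 | unknown |
| ungraded + Grade 3 | Grade 3 | unknown |
| ungraded + Grade 4 | Grade 4 | unknown |
| ungraded + Grade 5 | Grade 5 | Grade 5 |
| Grade 3 + Grade 4 | Grade 4 | Grade 4 |
| ungraded only | unknown | unknown |

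The rules differ in the first four rows. In the third and fourth, the subject still qualifies for the separate Grade 3-or-higher summaries, so the report can show the same child as high-grade in one table and 'unknown' in another.

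**Step 2. Causality.**

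| Occurrences | SAP Maximum Relationship | Protocol 6.1.3 rule |
|---|---|---|
| missing only | unknown | associated |
| missing + No Reasonable Possibility | unknown | associated |
| missing + Reasonable Possibility | Reasonable Possibility | associated |
| No Reasonable Possibility only | No Reasonable Possibility | not associated |

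The first two rows differ. A recorded 'Reasonable Possibility' is never displaced.

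**Step 3. Size.** Inputs: about 62 subjects in total (SAP 5.2) and at least 12 per age group in Part 1 (SAP 4.2). The shift from k reclassified subjects is 100 × k / N.

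- k = 1: 100 × 1/62 = 1.6 points; 100 × 1/12 = 8.3 points.
- k = 3: 100 × 3/62 = 4.8 points; 100 × 3/12 = 25.0 points.

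The range k = 1 to 3 is an assumption, because the documents give no frequency of missing grades or causality. If the displaced child was the only Grade 3 or 4 case for a term in a group of 12, the maximum-severity table would show 0% at those grades instead of 8.3%.

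**The case against.** A reader might infer that safety as a whole is understated, that both rules push in the reassuring direction, or that events without causality vanish from every drug-related count. The documents do not support any of these.

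- The severity rule is stated only for the maximum-severity tables. The Grade 3-or-higher summaries still count the child, and the child remains visible in the 'unknown' row.
- The severity rule displaces known Grades 1 and 2 as well as 3 and 4. The relationship rule takes subjects out of the 'No Reasonable Possibility' row and never overrides a known 'Reasonable Possibility'.
- Exclusion from the related-event summaries is an inference. The SAP does not say how those summaries handle missing causality, and a programmer could apply the protocol rule there.

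The sponsor has further arguments. A specific rule for missing grades may be read as overriding the general one. If one occurrence is ungraded, the true maximum is certain only when another is Grade 5. The relationship table is meant to show the investigator's view, whereas Protocol 6.1.3 states the sponsor's. Both documents say that no safety data are imputed (Protocol 8.1, SAP 6.3). Missing grades should also be uncommon, since investigators are required to grade every event.

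These arguments limit the point but do not remove it. Uncertainty about the maximum does not justify discarding a known minimum. The no-imputation sentence stands in the same protocol as the causality rule, so it does not cancel that rule; and SAP 11.2.1 itself assumes that an event with an incomplete onset date is treatment-emergent unless other evidence shows otherwise. The investigator-assessed basis is a fair reason to keep an 'unknown' row in the relationship table, but not to leave the related-event summaries silent.

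**Conclusion.** The point holds in two limited parts. In the maximum-severity tables only, a known Grade 3 or 4 can be removed from its row, against the SAP's own most-severe rule and out of line with its Grade 3-or-higher summaries. In the drug-related summaries, a literal reading gives counts that can be lower than Protocol 6.1.3 implies.

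Both parts depend on grades or causality being missing at analysis. The severity part also needs a second, graded occurrence of the same event in the same child. The sizes above are therefore per affected subject and do not forecast a bias. The change is worth making because the rules conflict as written and the repair is cheap.

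**What to change.** In SAP 11.2.1.1:

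- **Maximum Severity Grade Level:** classify each subject by the highest known grade for the term, and use 'unknown' only when no occurrence is graded.
- **Overview, SOC/PT and PT tables of related events:** count missing or non-assessable causality as related, as Protocol 6.1.3 states, and footnote how many were assigned this way.
- **Maximum Relationship:** either apply the same rule, or keep the investigator-assessed 'unknown' row with a footnote saying that these events are counted as related in the other tables.

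The cost is about two sentences of SAP text and a derivation change; no new data are needed. The downside is that related-event counts may be slightly less favourable.
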